Wbp Personal Data Protection Act (in Dutch: Wet Bescherming Persoonsgevens)

WMO Medical Research Involving Human Subjects Act (in Dutch: Wet Medisch-wetenschappelijk Onderzoek met Mensen)

SUMMARY

Rationale: Posterolateral spinal fusion is currently performed by using large amounts of autologous bone graft. Drawbacks of bone grafting include the need for an additional surgical procedure, limited supply, sub-optimal bone quality in osteoporotic patients and harvesting morbidity, which led to the development of numerous bone graft substitutes. Recently, we completed enrollment and one-year follow-up for a clinical trial to evaluate such a bone graft substitute (AxA study, METC number 13-192). The product, AttraX® Putty, is a bioresorbable tricalcium phosphate (TCP), mixed with a fast resorbing polymer carrier to improve surgical handling. The preliminary results are promising in terms of no adverse events related to the product and a first impression of similar fusion rates. However, especially in more challenging conditions, both the autograft and the material may resorb too fast and bone formation by induction was limited. Recently an improved version of the TCP granules has been developed, named MagnetOs™ Granules, which has shown favorable results especially of these resorption and induction characteristics in pre-clinical studies. MagnetOs™ Granules are CE-marked (2115660CE01) and received 510(k) clearance from the US Food and Drug Administration (K161859).

Objective: The primary objective is to demonstrate non-inferiority of MagnetOs™ Granules compared to autograft in instrumented posterolateral spinal fusion, in terms of efficacy and safety by means of an intra-patient model.

Study design: This study is designed as a multicenter, observer blinded, randomized, controlled non-inferiority trial with intra-patient comparisons.

Study population: 100 adult patients qualified for posterolateral spinal fusion in the thoracolumbar and lumbosacral region (T10-S2) will be recruited and enrolled in this study.

Intervention: According to a randomization scheme, one side of the spine will be grafted with the MagnetOs™ Granules and the other side with bone harvested from the iliac crest and local bone. The rest of the surgical procedure will be according to standard care.

Main study parameters/endpoints: The primary efficacy outcome is the rate of successful posterolateral spinal fusion after one year, assessed on CT-scans. Non-inferiority of the MagnetOs™ condition compared to the autograft condition will be assessed using a McNemar's test. The primary safety outcome is the number and nature of (serious) adverse events related to the surgical procedure compared to control populations from literature. Secondary outcomes are the comparison to its predicate (AttraX® Putty), relation between posterolateral fusion and interbody fusion after one-year, posterolateral spinal fusion rate after two years, relevance of iliac crest donor site pain and the incidence of long-term complication and relation with risk factors in the combined population of this study and the AxA study.

Nature and extent of the burden and risks associated with participation: Patient burden and risks are expected to be minimal. The first-year follow-up will be according to the

standard of care at the UMC Utrecht. Additional procedures for this study include the completion of short patient reported outcome measurements at five time points and, depending on the local follow-up protocol, a CT-scan at one-year follow-up and/or X-ray at two years follow-up. In case the one-year CT-scan shows a doubtful fusion or non-union in any of the relevant levels, an additional CT-scan will be made at two years follow-up. Based on pre-clinical investigations, and the results of the AxA study, the risk for inferior performance of MagnetOsTM Granules is expected to be minimal. Even if this appears to be the case, it will have minimal consequences for the patient as the other side of the spine will be fused with autologous bone graft and the spine is rigidly instrumented with screws and bars. All patients may benefit from the study in terms of reduced surgical time, since only half of the required bone graft will be harvested from the iliac crest.

1. INTRODUCTION AND RATIONALE

Spinal fusion is a surgical procedure frequently used for many spinal conditions requiring stabilization of the vertebral column, with or without correction of deformities. The primary surgical aim of this procedure is to establish bony fusion between one or more vertebral segments. Many fusion techniques are available ranging from anterior interbody fusion to posterior or posterolateral procedures and combinations of these. Especially in conditions of mechanical instability, the bony fusion is facilitated by rigid instrumentation of the vertebrae. Bony fusion will develop in time between the immobilized vertebrae when the bone surfaces are denuded and graft material is added. This process of fusion is a relatively slow process that takes months to years before complete fusion. Therefore, higher fusion rates are observed after one year as compared to six months. Autologous bone grafting (or autografting) with bone harvested from the iliac crest is the gold standard to achieve bony fusion. This is a reliable and well known technique for many indications.¹ Whether the bone formation after autografting is the result of direct bone formation from the graft, induction by the graft, or conduction of host bone remains a matter of debate.² It is a fact however, that alternatives like allograft and ceramics generally perform less good than autologous bone from the iliac crest. Bone morphogenic proteins (BMP-2, OP-1) were a popular alternative, however, these growth factors have been related to serious complications and may not perform as good as autograft.^{3,4} Especially when more extensive and challenging fusions are performed, large amounts of graft are required. This can be problematic since the amount of available bone graft from the iliac crest is limited and large quantities may lead to more morbidity.³ If extensive decompression is not required, fusion procedures on a single spinal level are nowadays often performed with less invasive techniques, combining interbody cages with relatively low amounts of bone graft and/or percutaneous pedicle screw instrumentation. The real value of an autograft bone substitute is therefore mainly for the more extensive surgical procedures where large amounts of autograft are required. Such cases include the treatment of multilevel spinal stenosis, primary or secondary scoliosis and other deformities. A graft substitute will reduce donor site morbidity and surgery time in those cases. At the same time, these conditions are less forgiving and require a graft substitute that has at least the same bone forming potential as the autograft. Consequently, the graft substitute has to perform like autograft in terms of both generating bone volume and bony fusion.

For decades, a suitable alternative to the autologous bone graft has been the subject of extensive research. Initially, allogeneic and xenogeneic bone grafts from a human donor and animal donor respectively were investigated. Although still very often applied, allogeneic grafts do not perform as good as autografts in many situations and they carry a theoretical

risk of disease transmission.⁵⁻⁷ Since the 1970s synthetic ceramics have been investigated as a more safe and predictable graft substitute. As most ceramics represent the anorganic mineral-phase of bone tissue, this strategy seems logical and attractive. Major concerns with ceramics are the brittleness and resistance to resorption and remodeling. An alternative is to use the organic-phase of donor bone, the so-called demineralized bone matrix (DBM). However, also this material has disadvantages of which unpredictable effectiveness is one of the major concerns.^{8,9} Since the 1990s, bone morphogenetic proteins (BMP's) have been introduced and applied at a large scale, especially in the United States. Most well-known are BMP-2 and BMP-7, which have shown effectiveness in several preclinical and clinical studies. However, these effects could only be accomplished when extremely high dosages were applied. These extreme doses may be the cause of the recently reported serious side effects.⁴

Since the late 1990s, a specific group of ceramics has been identified and developed that possesses osteoinductive activity in some animal models without the addition of any substance.^{10,11} The exact mechanism behind this characteristic has not yet been elucidated, but several important parameters like microporosity and surface characteristics have been identified.^{11,12} Furthermore, it has been shown that osteoinductive characteristics are associated with enhanced bone formation in several pre-clinical animal models.¹³ Such a ceramic has been commercialized under the name AttraX® Putty (NuVasive, San Diego, CA) and is investigated by us in a similar multicenter, randomized, controlled trial (AxA study, METC number 13-192). This study started in October 2013. The last patient was operated in July 2016 and one-year follow-up was completed in July 2017. A total of 108 patients were included and 100 patients were operated according to the study protocol. The current study will be according the same intra-patient design which has many advantages as explained below. The preliminary results of the AxA study indicate favorable results in terms of a perceived similarity between autograft and AttraX® Putty and the absence of product related (serious) adverse events. During the AxA study we did observe that, especially in challenging conditions with long fusion trajectories, both the autograft and AttraX® Putty placed around the instrumentation and in the posterolateral gutters resorbed too fast and intertransverse fusion did not occur, or only between the facet joints. That observation was confirmed by the steep reduction in graft density between 3 and 6 months observed with DEXA-scanning.

Recently the composition and manufacturing of AttraX (which was originally developed by Progentix Orthobiology, the Netherlands) has been changed by the same research group ([name] and [name], Kuros Biosciences BV, The Netherlands). These changes involve a higher hydroxyapatite (HA) content which causes a lower resorption rate, and a

surface modification which has shown more favorable osteoinductive activity in several studies, as well as less rapid resorption compared to autologous bone.¹⁴⁻¹⁸ In a preclinical posterolateral spinal fusion study in sheep, the fusion rate was comparable to autograft and not influenced by adding a binder.¹⁶ This new version has received a CE-mark (number 2115660CE01) followed by 510(k) clearance from the US Food and Drug Administration (FDA) under the name MagnetOsTM Granules and is produced by Kuros Biosciences BV.

The aim of the current study is to clinically investigate MagnetOsTM Granules as an alternative to autologous bone graft in adult patients qualified for instrumented posterolateral fusion of the thoracolumbar or lumbosacral spine by means of an intra-patient model. This patient population will benefit most from such a graft substitute. We expect that MagnetOsTM Granules will perform as good as autograft, while eliminating the morbidity and increased surgical time associated with harvesting of autologous bone from the iliac crest.

2. OBJECTIVES

2.1 Primary objectives

The primary objective of this study is to demonstrate the non-inferiority of MagnetOsTM Granules as compared to autologous bone graft in instrumented posterolateral fusion of the thoracolumbar and lumbosacral spine, in terms of efficacy and safety.

1. Efficacy will be based on the posterolateral spinal fusion rate assessed at one-year CT-scans;
2. Safety will be evaluated by documenting the number and nature of all (serious) adverse events that may in any way be related to the surgical procedure. The complication rate will be compared to the rate in control populations from literature.

2.2 Secondary objectives

1. To compare the quantitative primary and secondary results of MagnetOsTM Granules to the results of Attrax® Putty from the AxA study (unpaired);
2. To investigate the relation between successful posterolateral fusion and interbody fusion, assessed at the one-year CT-scans used for the primary objective;
3. To compare the posterolateral spinal fusion rate of both MagnetOsTM Granules and autograft at one year with the fusion rates after two years, by using CT-scans;
4. To investigate the effect of blinding on perceived donor site pain, based on outcome measures reported by patients unblinded to the iliac crest donor site in comparison to these outcomes of the blinded patients from the AxA study;
5. To combine the study populations of the current study and the AxA study to investigate a) adjacent segment disease, in relation to length of construct and sagittal balance and b) risk factors for failures.

2.3 Rationale for secondary objectives

Besides the primary research question on efficacy and safety, this study gives the opportunity to investigate very relevant scientific questions that can only be answered in human patients. Furthermore, combining the study data with the data obtained from the AxA study increases the power to study phenomena that occur less frequently.

1. Comparison of the quantitative results of MagnetOsTM Granules to Attrax® Putty

Since both the study designs are the same and have the same in- and exclusion criteria, it will be possible to compare the groups in a standard unpaired fashion. We did not power this comparison since it is a secondary aim, but the findings will be indicative with a considerable

sample size of 200 individuals (each with autograft at one side of their spine and MagnetOs™ Granules (n=100) or AttraX® Putty (n=100) at the other side).

2. Relation between posterolateral fusion and interbody fusion

Since this study will not exclude interbody fusions, and the effect of such interbody fusions on the posterolateral fusion masses is unknown, it is desired to determine the statistical relation between the posterolateral and interbody fusions.

3. Fusion rate after 2 years

There are indications that the percentage bony fusion continues to increase between 1 and 2 years.²⁶⁻²⁸ Whether this is graft related or a result of immobilization due to instrumentation is unclear. Nevertheless, it is important to determine the long-term fusion potential and behavior of MagnetOs™ Granules and autograft, and to compare these conditions. To limit the number of CT-scans at 2 years follow-up, only those patients that scored a doubtful fusion or non-union in any of the relevant levels at the one-year CT-scan will undergo an additional CT-scan.

4. Relevance of donor site pain

Although iliac crest donor site morbidity is often reported by patients, the relevance of donor site pain is disputable when the bone is harvested via the same incision as used for the spinal fusion.³ The preliminary results of the AxA study indeed indicate that there is no relation between the real donor site and the iliac crest that is indicated by blinded patients. To determine if the often reported high incidence of donor site pain can be explained by the knowledge of the patient where the bone graft was taken, we will not blind the patients for the donor site in this study. The outcomes measures reported by patients unblinded to the iliac crest donor site will be compared to the outcomes of the blinded patients from the AxA study.

5. Combine the study populations of the current study and the AxA study

To combine the study data of both the current study and the AxA study will allow investigations on more infrequent phenomena on a relatively large population. Such a phenomenon is for example adjacent segment disease. This is a longterm complication where the adjacent joints and intervertebral disc may wear faster and cause degenerative disease. The occurrence of adjacent segment disease may be related to length of the construct and restoration of the sagittal balance. The occurrence of typical complications like infection and pseudoarthrosis can be related to risk factors like comorbidities, smoking, length of instrumented segment and so on.

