9.1 Primary efficacy analysis

For the primary efficacy analysis, a comparison will be made between the fusion performance of the MagnetOsTM condition and the autograft condition, scored from the one-year (12-15 months) CT-scans according to the method described in Appendix C. Patients that required revision surgery influencing the fusion will be excluded from this analysis. In addition, if one side of a fusion-level is considered not evaluable, this level will be excluded. All evaluable scores will be dichotomized into fusion and no fusion. To allow inclusion of patients with fusion of multiple segments, without increasing the influence of these patients on the outcome, each side in these patients will be statistically considered as one condition. This means that the possible outcomes in these patients are: no fusion (if none of the levels is fused), equal fusion (if an equal number of segments is fused per side) or fusion at one side vs. no-fusion at the other side in case one side contains more fused segments than the other side.

The basis for the primary efficacy analysis will be the test of non-inferiority by performing a McNemar's test. The null hypothesis is that inferiority in fusion rate of the MagnetOsTM Granules compared to the autograft condition is greater than 15% (PAG-PMAG \geq 15%); the alternative hypothesis is that the MagnetOsTM Granules fusion rate will not be lower than the autograft success rate by more than 15% (PAG-PMAG< 15%).

In addition to the McNemar's test, a generalized estimating equations (GEE) model will be used to examine fusion on each side of a vertebra, while accounting for clustering of vertebrae within patients. The outcome will be fusion (yes/no) and the explanatory variable will be treatment. Analysis will result in an odds ratio for MagnetOsTM Granules vs. autograft and a 95% confidence interval.

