9.3 Analysis of secondary outcomes

1. To compare the quantitative primary and secondary results of MagnetOs™ Granules to Attrax® Putty a McNemar's test will be used as well as the mentioned GEE model;
2. As mentioned for the primary analysis, the odds-ratios and 95% confidence intervals for fusion rates of MagnetOs™ Granules and autograft will be calculated by using the GEE model. This model also allows to assess the effect of an additional interbody fusion;
3. For the comparison of the fusion rate after two years, the same method as for the primary efficacy analysis will be used;
4. VAS pain scores will be analyzed using the paired t-test, or Wilcoxon signed rank test in case of not-normally distributed data. To investigate the effect of blinding on perceived donor site pain, pain scores reported by the patients of this study and the AxA study will be compared using the unpaired t-test or Mann-Whitney U test.
5. To investigate risk factors of both study populations regression analysis will be done.

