APPENDIX C. CT ASSESSMENT

Aim

To compare the fusion rate of the MagnetOsTM granules side to the autograft side after 1 and 2 years, by using CT-scans.

Method primary analysis

For the primary analysis, all included patients will be CT-scanned at the treating center. The CT-scan will be scheduled at 12-15 months after surgery. The standard local protocol for the spine will be used when this provides a slice thickness of ≤ 1 mm. Otherwise, the slice thickness will be adapted. To allow all desired planar reconstructions, the data will be captured and stored as volume scans. The raw volume dataset (DICOM scans), and preferably reconstructions in the coronal, sagittal and axial, will be de-identified and stored on a CD-ROM and send to the principal investigator for assessment by a panel consisting of at least one spine surgeon and an uninvolved specialist. Based on literature review and experience with the AxA trial we developed the following protocol.

Stepwise protocol

- All patients will be scanned with a volume scan with ≤ 1 mm slice thickness;
- Data will be captured and stored as volume scans;
- All scans will be assessed independently by at least two observers, blinded to the treatment allocation;
- First, the fusion level and side will be identified and assessed in three planes: coronal, sagittal and axial;
- Osteotomized segments will be excluded from the analyses. If one side of a fusion-level is considered not evaluable, this level will be excluded as well;
- If obvious indications of mobility like material failure or apparent pseudoarthrosis exist, the level will be considered a non-union;
- If not, the presence of an obvious bone bridge/fusion between the posterolateral vertebra will be determined;
- Fusion is scored based on assessment in three planes and at two locations, to indicate the probability that the bony bridge is graft related:
 - Likely graft related is a bony bridge between the transverse process and >1 mm lateral or above the rod;
 - Probably not graft related is a bone bridge directly around the rod, between the lamina or fusion of the facet joints;

- An obvious fusion at any of these locations in each plane is scored 2 points, doubtful fusion is 1 point and non-union is 0 points;
- If the segment is fused in at least one plane (2 points) and does not show obvious absence of fusion in both the other planes (scores at least 1 in at least one of the other planes) it is regarded as fused;

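### The MagnetOs versus AttraX comparison does not separate a difference between the two trials from a difference between the products, although every patient in both trials has an autograft side

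*Combined protocol and SAP*

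**What the plan says.** Section 2.2 item 1 and Section 7.1.2 item 1 list the comparison with AttraX results from AxA first among the secondary objectives and outcomes, and label it unpaired. Section 2.3 item 1 gives the reason: "Since both the study designs are the same and have the same in- and exclusion criteria", so "it will be possible to compare the groups in a standard unpaired fashion". It counts 200 people, "each with autograft at one side of their spine", but gives that side no role in the comparison. On precision it says "We did not power this comparison since it is a secondary aim" and presents the findings as indicative.

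Section 9.3 item 1 gives the method: "a McNemar's test will be used as well as the mentioned GEE model". Section 9.1 specifies that model: "The outcome will be fusion (yes/no) and the explanatory variable will be treatment". Section 9.3 item 2 and Appendix A allow interbody fusion as a further factor. No section adds a trial term or a graft-by-trial term, or plans to check whether autograft fusion agrees between the trials.

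On CT reading, Appendix C says "Based on literature review and experience with the AxA trial we developed the following protocol". It does not say whether AxA scans were, or will be, read under those rules.

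**The concern.** MagnetOs and AttraX were never randomised against each other. According to the Introduction, AxA surgery ran from October 2013 to July 2016, before this trial. Equal eligibility criteria do not guarantee equal case mix when one to six levels between T10 and S2, with or without interbody devices, are eligible. The protocol makes this argument itself: its rationale for the intra-patient design is that such patients and procedures are hard to compare, and that each patient should therefore be the control.

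If fusion on both sides is higher in one trial because of patients, surgery or reading, an analysis that ignores trial credits some of that to the product. The comparison could then show a product difference that does not exist, or hide a real one. Being unpowered concerns precision. It does not protect against this bias.

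McNemar's test does not fit either. It needs pairs, and no patient has both products.

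**Working it through.** **1. Inputs.** From Section 4.4: 50% fusion per side, 70% concordance (so 30% discordance), 100 enrolled and about 15% not evaluable, hence 85. Assumed: 85 evaluable in AxA too, one level per patient, no product effect, and a shift δ common to both sides of one trial. The documents give no value for δ, so a range is shown.

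**2. The plan's own figure.** No sample size is stated for this comparison. For the primary one, the Wald formula gives (1.645 + 0.842)² × 0.30 / 0.15² = 82.4, so 83. Exact enumeration of the score test at n = 84 gives power 0.80098, as printed in Appendix A. Dropout: 84 / 0.85 = 98.8, so 99, rounded to 100. The inputs are therefore read as intended.

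**3. Standard errors.**
- Raw product rates: √(2 × 0.25 / 85) = 7.7 points.
- Difference between trials in the within-patient difference: √(2 × 0.30 / 85) = 8.4 points.
- Ratio: √(0.30 / 0.25) = 1.10.

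**4. Raw unpaired test, two-sided 5%.** The false-positive rate is Φ(δ/7.67 − 1.96) + Φ(−δ/7.67 − 1.96), with δ in points.

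| δ (points) | Raw test | Anchored |
|---|---|---|
| 5 | 10% | 5% |
| 10 | 26% | 5% |
| 15 | 50% | 5% |
| 20 | 74% | 5% |

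**5. Pooled GEE without a trial term.**
- At 50% fusion both sides fuse in 35% of patients, so the within-patient correlation is (0.35 − 0.25) / 0.25 = 0.40.
- The model forces one autograft mean on both trials. Each product mean is adjusted by 0.40 times its trial's autograft deviation, which leaves (1 − 0.40)δ = 0.60δ in the product contrast.
- Its standard error is √(2 × 0.25 × (1 − 0.40²) / 85) = 7.0 points.
- At δ = 10 the bias is 6 points and the approximation gives 14% false positives. Simulating the GEE (500 runs) gives 16%.
- At δ = 20 the figures are 40% and 38%.
- With a trial term added, the simulated rates are 5.6% and 4.8%.

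**6. Price of anchoring.**
- Difference detectable with 80% power (2.80 × SE): 23.5 points against 21.5.
- Power for a true 20-point difference: Φ(20/8.40 − 1.96) = 66%. The raw test has 74% on the same fixed variances, or 76% by the two-proportion formula at 50% against 70%.
- The price rises with discordance: at 40% the anchored standard error would be √(2 × 0.40 / 85) = 9.7 points.

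**The case against.** The strongest reply is that unpaired may mean only that the two products sit in different people. The results to be compared could then be the within-patient ones, and an unpaired comparison of within-patient differences would fit the sentence. That stands as a possible reading. But no section states that contrast, and the model named carries treatment alone.

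A reader might infer that any difference between the trials passes whole into the product effect and that the autograft sides are discarded. The documents do not support this, for two reasons. If the trials are pooled, the GEE contains the autograft sides and absorbs about 40% of a shift. In multilevel patients the score of Section 9.1 and Appendix A is already partly relative to the other side. Simulated with two to four levels, equal non-zero counts scored as fused on both sides and about 70% concordance per level, a 10-point shift becomes roughly 3 to 8.5 points, with raw false positives of about 7% to 21%. The level mix is not given. The 26% therefore belongs to a single-level two-proportion test that the plan does not name. Neither feature is presented as a control for trial differences, and neither removes the bias.

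A reader might also infer that AxA scans were read by other rules. Appendix C shows only that AxA experience informed the present rules. The shared design, eligibility and established cooperation with the other centres point towards similarity, so the true shift may be small.

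**Conclusion.** The concern holds as a gap in the analysis of the first secondary objective: followed as written, the plan cannot tell a trial-wide difference from a product difference. Under the stated assumptions, a 10-point shift gives about 26% false positives in a raw test and about 16% in a pooled treatment-only GEE, against about 5% when anchored. In multilevel patients the raw figure would be lower. The shift itself is assumed, and nothing in the documents shows that one exists.

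Severity is low to moderate. The comparison is secondary, unpowered and offered as indicative, and the primary within-patient analysis is untouched. Swapping McNemar's test for an ordinary unpaired test would fix the mismatch of test and data, but would leave this gap open.

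**What to change.** In Section 2.3 item 1 and Section 9.3 item 1:

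- Delete McNemar's test for this comparison.
- Define the contrast as MagnetOs minus autograft in this trial against AttraX minus autograft in AxA.
- Name one primary estimand, for example the unpaired comparison of within-patient risk differences. Make the GEE graft-by-trial term supportive. It is on the odds-ratio scale and can disagree when baseline rates differ, so the two are not interchangeable.
- Report the autograft fusion rate in each trial, and show raw product rates as description only.
- State whether AxA scans are read under Appendix C.

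This takes a few sentences and one model term, with no new patients or visits. Patient-level AxA data are needed, and Section 2.2 item 5 already plans to combine the two populations. The statistical cost is a standard error about 10% larger (8.4 against 7.7 points), with power for a true 20-point difference of about 66% against 76%. Anchoring removes only shifts common to both sides on the chosen scale. A trial difference that affects autograft and substitute unequally would remain.
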